**6.3.4. Visit 3 – Week 6**

The following procedures will be performed at the Week 6 visit:

1. Review concomitant medications
2. C-SSRS
3. EQ-5D-5L
4. Vital signs:
  - a. HR, SBP, and DBP

- b. RR and body temperature
5. Dosing Diary collection and review
6. Incidence of Falls Diary collection and review
7. Midodrine Diary collection and review
8. AE assessment (AEs, SAEs, AESIs)
9. Collect, review, and dispense study drug

#### **6.3.5. Visit 4 – Week 10**

The following procedures will be performed at the Week 10 visit:

1. Review concomitant medications
2. C-SSRS
3. [REDACTED]
4. Vital signs
  - a. HR, SBP, DBP
  - b. RR and body temperature
5. Physical examination
6. Neurological examination
7. 12-lead ECG (in triplicate separated by at least 1 minute for each replicate, after the subject has been resting for at least 5 minutes)
8. Pregnancy test (in women of childbearing potential only)
9. Blood collection: Hematology, Chemistry
10. Urine collection: Urinalysis
11. Dosing Diary collection and review
12. Incidence of Falls Diary collection and review
13. Midodrine Diary collection and review
14. AE assessment (AEs, SAEs, AESIs)
15. Collect, review, and dispense study drug

#### **6.3.6. Telephone Contact 1 – Week 14**

The following procedures will be performed at Week 14:

1. Review concomitant medications
2. AE assessment (AEs, SAEs, AESIs)

#### **6.3.7. Visit 5 – Week 18**

The following procedures will be performed at the Week 18 visit:

1. Review concomitant medications
2. C-SSRS

3. [REDACTED]
4. Vital signs
  - a. HR, SBP, DBP
  - b. RR and body temperature
5. Dosing Diary collection and review
6. Incidence of Falls Diary collection and review
7. Midodrine Diary collection and review
8. AE assessment (AEs, SAEs, AESIs)
9. Collect, review, and dispense study drug

**6.3.8. Telephone Contact 2 – Week 22**

The following procedures will be performed at Week 22:

1. Review concomitant medications
2. AE assessment (AEs, SAEs, AESIs)

**6.3.9. Visit 6 – Week 26**

The following procedures will be performed at the Week 26 visit.

1. Review concomitant medications
2. C-SSRS
3. [REDACTED]
4. Vital signs
  - a. HR, SBP, DBP
  - b. RR and body temperature
5. Physical examination
6. Neurological examination
7. 12-lead ECG (in triplicate separated by at least 1 minute for each replicate, after the subject has been resting for at least 5 minutes)
8. Pregnancy test (in women of childbearing potential only)
9. Blood collection: Hematology, Chemistry
10. Urine collection: Urinalysis
11. Dosing Diary collection and review
12. Incidence of Falls Diary collection and review
13. Midodrine Diary collection and review
14. AE assessment (AEs, SAEs, AESIs)
15. Collect, review, and dispense study drug

### **6.3.10. Early Termination Up to Week 26**

Subjects terminating the study prior to Week 26 will complete all of the following procedures.

1. Review concomitant medications
2. C-SSRS
3. [REDACTED]
4. Vital signs
  - a. HR, SBP, DBP
  - b. RR and body temperature
5. Physical examination
6. Neurological examination
7. 12-lead ECG (in triplicate separated by at least 1 minute for each replicate, after the subject has been resting for at least 5 minutes)
8. Pregnancy test (in women of childbearing potential only)
9. Blood collection: Hematology, Chemistry
10. Urine collection: Urinalysis
11. Dosing Diary collection and review
12. Incidence of Falls Diary collection and review
13. Midodrine Diary collection and review
14. AE assessment (AEs, SAEs, AESIs)
15. Collect and review study drug

### **6.3.11. Visit 7 – Week 38**

The following procedures will be performed at the Week 38 visit:

1. Review concomitant medications
2. AE assessment (AEs, SAEs, AESIs)
3. Collect, review, and dispense study drug

### **6.3.12. Visit 8 – Week 50**

The following procedures will be performed at the Week 50 visit:

1. Review concomitant medications
2. Pregnancy test (in women of childbearing potential only)
3. AE assessment (AEs, SAEs, AESIs)
4. Collect, review, and dispense study drug

**6.3.13. Telephone Contact 3 – Week 62**

The following procedures will be performed at Week 62:

1. Review concomitant medications
2. AE assessment (AEs, SAEs, AESIs)

**6.3.14. Visit 9 – Week 74**

The following procedures will be performed at the Week 74 visit:

1. Review concomitant medications
2. Pregnancy test (in women of childbearing potential only)
3. AE assessment (AEs, SAEs, AESIs)
4. Collect, review, and dispense study drug

**6.3.15. Telephone Contact 4 – Week 86**

The following procedures will be performed at Week 86:

1. Review concomitant medications
2. AE assessment (AEs, SAEs, AESIs)

**6.3.16. Visit 10 – Week 98**

The following procedures will be performed at the Week 98 visit:

1. Review concomitant medications
2. Pregnancy test (in women of childbearing potential only)
3. AE assessment (AEs, SAEs, AESIs)
4. Collect, review, and dispense study drug

**6.3.17. Telephone Contact 5 – Week 110**

The following procedures will be performed at Week 110:

1. Review concomitant medications
2. AE assessment (AEs, SAEs, AESIs)

**6.3.18. Visit 11 – Week 122**

The following procedures will be performed at the Week 122 visit:

1. Review concomitant medications
2. Pregnancy test (in women of childbearing potential only)
3. AE assessment (AEs, SAEs, AESIs)
4. Collect, review, and dispense study drug

**6.3.19. Telephone Contact 6 – Week 134**

The following procedures will be performed at Week 134:

1. Review concomitant medications
2. AE assessment (AEs, SAEs, AESIs)

**6.3.20. Visit 12 – Week 146**

The following procedures will be performed at the Week 146 visit:

1. Review concomitant medications
2. Pregnancy test (in women of childbearing potential only)
3. AE assessment (AEs, SAEs, AESIs)
4. Collect, review, and dispense study drug

**6.3.21. Telephone Contact 7 – Week 158**

The following procedures will be performed at Week 158:

1. Review concomitant medications
2. AE assessment (AEs, SAEs, AESIs)

**6.3.22. Visit 13 – Week 170**

The following procedures will be performed at the Week 170 visit:

1. Review concomitant medications
2. AE assessment (AEs, SAEs, AESIs)
3. Collect, review, and dispense study drug

**6.3.23. Visit 14 – Week 182/End of Treatment/Early Termination after Week 26 through Week 182**

Subjects who complete the 182-week treatment period, or terminate the study early after Week 26 will complete all End of Treatment visit procedures.

1. Review concomitant medications
2. Pregnancy test (in women of childbearing potential only)
3. AE assessment (AEs, SAEs, AESIs)
4. Collect and review study drug

**6.3.24. Telephone Contact 8 – Week 184/Follow-up**

The Follow-up visit must be completed within 2 weeks (+/- 7 days) from the date of the last dose for all subjects who complete the 182-week treatment period or terminate the study early at any point during the study. The following procedures will be performed at the Follow-up visit.

1. Review concomitant medications
2. AE assessment (AEs, SAEs, AESIs)

## 6.4. Description of Study Assessments

Written informed consent must be obtained prior to performing any protocol specific procedures. After providing full informed consent, subjects will undergo a medical screen to determine their eligibility for participation based on the criteria outlined in this protocol.

The site should make every effort to perform procedures at the scheduled times, and information should be recorded in the source documents and on the CRFs. All subject reported outcomes for subjects with PD should be completed in an ON state, and within 1-4 hours of taking the PD medications.

Additional safety tests, such as vital signs (BP, HR, RR, and body temperature), physical examinations, ECGs, and laboratory safety assessments, may be obtained during the course of the study on the basis of newly available data to ensure appropriate safety monitoring.

### 6.4.1. Demographic and Baseline Assessments

Demographic information to be collected will include: year of birth, sex, race, and ethnicity.

The data will be confirmed with information captured in Study 0170.

### 6.4.2. [REDACTED]

[REDACTED]

[REDACTED]

[REDACTED]

[REDACTED]

### 6.4.3. Safety Assessments

#### 6.4.3.1. Columbia-Suicide Severity Rating Scale

The C-SSRS is a tool designed to systematically assess and track suicidal AEs (suicidal behavior and suicidal ideation). The strength of this suicide classification system is in its ability to comprehensively identify suicidal events while limiting the over-identification of suicidal behavior. The C-SSRS Since Last Visit Version will be used for all visits.

Assessments will be performed as specified in the Schedule of Study Procedures (Table 1). An example of the instrument is provided in Appendix 1.

#### **6.4.3.2. Adverse Events**

Study 0171 AEs will be reviewed and recorded from date of first dose of study drug through the end of follow-up. Adverse events may be observed by the site study personnel or spontaneously reported by the subject or subject's caregiver. In addition, ongoing AEs from preceding Study 0170 will be followed in this study.

Adverse events that start after signing of Study 0171 informed consent, but before the first dose of study drug is taken on Day 2, are to be captured in Study 0170 database. Adverse events started in Study 0170 but which worsen in severity or seriousness during Study 0171 should be reported as a new adverse event.

All AEs must be recorded in the subject's CRF and, if applicable, reported as described in Section 7.

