#### **6.4.3.3. Medication and Medical History**

A complete medical history will be taken during Study 0170 and will include evaluation of past and present cardiovascular, respiratory, GI, renal, hepatic, neurological, endocrine, lymphatic, hematologic, immunologic, dermatologic, psychiatric, genitourinary, substance abuse, surgical history, or any other diseases or disorders. Medical conditions will be recorded for 2 years prior to screening visit, along with the date of diagnosis, and any other relevant medical history that has an impact to the subject.

Medical events or conditions that arise or worsen in severity or frequency after date of first dose of study drug will be recorded as an AE in Study 0171.

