#### **6.4.3.5. Neurological Examination**

Any abnormalities identified at Visit 1 will be recorded as neurological medical history. Any abnormalities or symptoms reported during treatment that arise or worsen in severity or frequency will be reported as AEs.

The examination will assess the following:

- Cranial nerves (cranial nerves II-XII, excluding funduscopic examination)
- Motor system (tone, strength, and abnormal movements)
- Sensory system (light touch, pinprick, joint position, and vibration)
- Reflexes (deep tendon reflexes and plantar responses)
- Coordination (upper and lower extremities)
- Gait (base and tandem gait)
- Station (posture and stability)

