#### 7.1.1. Adverse Events (AE)

An AE is any untoward medical occurrence in a patient or clinical trial subject administered a pharmaceutical product that does not necessarily have to have a causal relationship with this treatment. An AE can therefore be any unfavorable and unintended sign (including an abnormal laboratory finding), symptom, or disease temporally associated with the use of a medicinal product, whether or not related to the medicinal product.

- AEs may be new events.
- Pre-existing events that increase in frequency, severity or change in nature or seriousness during or as a consequence of participation in clinical studies.
- Pre- or post-treatment complications that occur as a result of a protocol-mandated procedure (such as a biopsy).
- AEs may be clinically significant changes from baseline in physical examination, laboratory tests, or other diagnostic investigation (e.g., laboratory results, x-ray findings).
- AEs may result from an overdose of the study drug.

Whenever possible, the diagnosis (rather than a series of terms related to a diagnosis) should be recorded as the AE term.

An AE does not include the following:

- Medical or surgical procedures (such as surgery, endoscopy, tooth extraction, or transfusion); the condition that leads to the procedure is an adverse event.
- Preexisting diseases or conditions present or detected before signing an informed consent form that do not worsen.
- Situations where an untoward medical occurrence has not occurred (such as hospitalization for elective surgery or social and/or convenience admissions).
- Overdose of either study drug or concomitant medication without any signs or symptoms, unless the subject is hospitalized for observation.

Any medical condition or clinically significant laboratory abnormality with an onset date prior to the date of first dose in Study 0171, is considered to be preexisting and should be documented in the medical history CRF.

Pregnancy is not an AE; however, if a female subject becomes pregnant during the conduct of the study, Theravance Biopharma, Inc. (TBPH) will be notified according to the procedures for SAE reporting as outlined in Section 7.4.3. Follow-up information regarding the outcome of the pregnancy and any fetal or neonatal sequelae will be obtained and documented.

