### 8.5.1. [REDACTED]

### 8.5.2. Adverse Event Data

Adverse events will be coded to the preferred terms of the Medical Dictionary for Regulatory Activities (MedDRA®). Summaries will present by system organ class (SOC), preferred term (PT) and severity, the frequency and percentage of subjects reporting each observed event.

A treatment-emergent adverse event (TEAE) will be defined as any AE that begins on or after the date of first dose of study drug up to the date of last dose of study drug plus the number of days in the follow-up period.

The number and percentage of subjects who experience TEAEs will be summarized. Summaries of TEAEs will include the following:

- [REDACTED]
- [REDACTED]
- [REDACTED]

[REDACTED]

[REDACTED]

[REDACTED]

[REDACTED]

[REDACTED]

All AEs reported will be listed by subject. A listing will be provided for all subjects who experience an SAE. Listings will also be provided for subjects who discontinued study treatment prematurely because of AEs and subjects who temporarily interrupted study treatment because of AEs. The AESIs, as described in Section 7.1.4 will be listed and summarized.

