### 8.1. Adverse Events

Adverse events are collected from signing of the informed consent form through the end of the study. Adverse events will be coded to the preferred terms of the Medical Dictionary for Regulatory Activities (MedDRA®, version 24.1).

A treatment-emergent adverse event (TEAE) will be defined as any AE that begins on or after the date of first dose of Study 0171 study drug up through 14 days after the date of last dose of study drug. AEs that begin more than 14 days after the date of last dose of study drug and AEs that begin during the period from obtaining informed consent to the start of administration of study drug will not be considered treatment-emergent and will be listed only.

The following AE summaries will be provided:

- TEAE overall summary
- TEAEs by preferred term
- TEAEs by system organ class and preferred term
- Moderate or severe TEAEs by system organ class and preferred term
- TEAEs by preferred term with frequency > 3% of safety analysis set subjects
- TEAEs by system organ class, preferred term, and severity
- Drug-related TEAEs by system organ class and preferred term
- Drug-related TEAEs by system organ class, preferred term, and severity
- Drug-related moderate or severe TEAEs by system organ class and preferred term
- Serious TEAEs by system organ class and preferred term
- Drug-related serious TEAEs by system organ class and preferred term
- TEAEs resulting in on-study deaths
- TEAEs leading to premature study drug discontinuation
- TEAEs leading to temporary interruption of study drug
- TEAEs of special interest by system organ class and preferred term (Section 8.1.1)

If no adverse events meeting a specific table definition were reported, the body of the table will contain only a statement that no events met the table definition.

The following AE listings will be provided:

- TEAEs
- AEs leading to premature study drug discontinuation
- AEs resulting in temporary interruption of study drug
- Serious adverse events
- Deaths
- Non-treatment-emergent adverse events

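### The rule for adverse events carried over from Study 0170 does not mention frequency, so a carried-over event that becomes more frequent can drop out of the TEAE and AESI summaries

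*Protocol*

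**What the plan says.** Four places in the protocol say when an existing event becomes an adverse event of Study 0171.

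- Section 6.4.3.2, specific to events from the feeder study: "Adverse events started in Study 0170 but which worsen in severity or seriousness during Study 0171 should be reported as a new adverse event". The same section says that "ongoing AEs from preceding Study 0170 will be followed in this study".
- Section 6.4.3.3, on medical events and conditions: those that "arise or worsen in severity or frequency after date of first dose of study drug will be recorded as an AE in Study 0171".
- Section 6.4.3.5, on the neurological examination: "Any abnormalities or symptoms reported during treatment that arise or worsen in severity or frequency will be reported as AEs".
- Section 7.1.1, the general AE definition, includes: "Pre-existing events that increase in frequency, severity or change in nature or seriousness during or as a consequence of participation in clinical studies". It adds that a condition with onset before the first Study 0171 dose "is considered to be preexisting and should be documented in the medical history CRF".

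The analysis side depends on onset date. Protocol 8.5.2 states: "A treatment-emergent adverse event (TEAE) will be defined as any AE that begins on or after the date of first dose of study drug". SAP 8.1 states: "A treatment-emergent adverse event (TEAE) will be defined as any AE that begins on or after the date of first dose of Study 0171". Its window closes 14 days after the last dose. Neither definition has a clause for worsening of an event that began earlier. All 15 AE summaries listed in SAP 8.1 are TEAE summaries, and SAP 8.1.1 summarises the incidence of treatment-emergent AESIs.

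**The concern.** Every subject rolls over from Study 0170, so any AE ongoing at entry is subject to these rules. By 7.1.1 it is also a pre-existing condition, so one event falls under two sets of rules with different triggers. For an intermittent event, worsening may show as more episodes rather than as worse ones, and that is the trigger missing from 6.4.3.2.

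Long-term safety is the primary objective. Scheduled vital signs, ECGs, laboratory tests and diaries stop at Week 26, after which the protocol's safety assessments are AEs and concomitant medications. From then on, AE recording is the main route by which a rising frequency of an existing event would be seen. If the event stays under its Study 0170 onset date, the tables carry no trace of the change. Where this happens, the effect can only lower TEAE counts relative to what 7.1.1 would give.

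**Working it through.** The plan gives no figure to reproduce. The check is a comparison of texts, followed by tracing one event through the definitions.

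**Triggers for a new or recordable AE**

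| Protocol section | Applies to | Severity | Frequency | Seriousness | Nature |
|---|---|---|---|---|---|
| 6.4.3.2 | AEs begun in Study 0170 | yes | not named | yes | not named |
| 6.4.3.3 | medical events or conditions | yes | yes | not named | not named |
| 6.4.3.5 | neurological abnormalities or symptoms | yes | yes | not named | not named |
| 7.1.1 | pre-existing events in general | yes | yes | yes | yes |

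**One event traced through**

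1. A subject enters Study 0171 with an intermittent AE from Study 0170, carried as a single open record.
2. Episodes become more frequent on TD-9855. Severity and seriousness do not change.
3. A site working from 6.4.3.2 finds neither named trigger met. The record continues with its Study 0170 onset date.
4. The TEAE definitions require onset on or after the first Study 0171 dose. The record fails this in both documents.
5. The event is absent from all 15 summaries in SAP 8.1 and, if it is an AESI, from the summary in SAP 8.1.1.
6. A site working from 6.4.3.3 or 7.1.1 records the same event as a Study 0171 AE. With an on-treatment onset date it is a TEAE and enters the tables.

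**Where else the event might appear.** SAP 8.1 provides a listing of non-treatment-emergent AEs and SAP 7.4 a medical history summary. The first gives no incidence, and the second describes conditions at entry rather than change on treatment.

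**Size per subject.** SAP Section 2 gives 110 enrolled. The size of the safety set is not stated, so taking it as 110 is an assumption; a smaller set would make each subject count slightly more.

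- One subject: 1/110 = 0.9%.
- Cut-off for the table of TEAEs above 3%: 0.03 × 110 = 3.3, so at least 4 subjects are needed (4/110 = 3.6%; 3/110 = 2.7%).

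One uncounted subject can therefore move a preferred term below that cut-off. The term would still appear in the full table by preferred term, with a count lower by one. The 0.9 points apply to a given row only if the subject has no other TEAE in that row. They apply to overall TEAE incidence only if the subject has no other TEAE at all.

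**The case against.** The strongest reply is that the four passages do not flatly contradict each other. Section 6.4.3.2 does not restrict new AEs to its two triggers; it is silent on frequency. Sections 6.4.3.3 and 6.4.3.5 are also incomplete, since both omit seriousness, yet nobody would read them as excluding an event that becomes serious. All three can be read as partial statements of 7.1.1, and 6.4.3.2 itself refers to Section 7. A site reading the protocol as a whole would record the more frequent event, and the onset-based TEAE definition would then count it.

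Much of this stands. A reader might infer that 6.4.3.2 forbids recording an increase in frequency; its wording does not support that. A reader might also infer that all recurrent falls, pressure rises or arrhythmias are lost. They are not: separate episodes entered with their own on-treatment onset dates are TEAEs, and AESIs are queried at each visit. Through Week 26, falls and near-falls are also counted from diaries, and blood pressure and ECG outliers are tabulated separately.

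It is also fair that adding a worsening clause to the TEAE definition would not be enough. Protocol 7.3 names onset and resolution dates, severity, relationship, outcome and action taken as recorded AE items; it names neither a frequency nor a date of worsening. Such a clause would have nothing to work on without new data.

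What remains is that the sentence specific to carried-over events is the one that omits frequency, and a site following it as written has no instruction there to open a new record.

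**Conclusion.** The concern holds in a limited form. The recording rules differ on whether increased frequency alone makes a carried-over event a new AE, and the onset-based TEAE definitions pass that difference through to every TEAE and AESI summary. The gap covers an event kept open as one continuing AE that becomes more frequent, without greater severity or seriousness, at a site that applies 6.4.3.2 rather than 6.4.3.3 or 7.1.1.

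The number of such subjects cannot be derived from the documents, so no total understatement of incidence can be given. A reader might infer a shortfall of several percentage points, or that sites did in fact record differently; the documents show that both are possible and establish neither. The supportable size is about 0.9 percentage points per affected subject, assuming a safety set of 110 and no other TEAE for that subject in the same category. The direction is known: against 7.1.1, counts can only be too low. The difference in wording is certain; its effect on the tables is possible.

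**What to change.** Align Protocol 6.4.3.2 with 7.1.1, so that a carried-over AE that increases in severity, frequency or seriousness, or changes in nature, is reported as a new AE with onset at the date of worsening.

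The study was terminated early, so that edit alone will not correct records already made. SAP Section 5 still places data cleaning and lock ahead. Before lock, query the AEs ongoing at Study 0171 entry for worsening after the first dose, naming frequency explicitly, and obtain its date. State in SAP 8.1 that events confirmed in this way are entered as new records with that onset date and so count as TEAEs under the existing definition.

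The cost is one sentence in the protocol, one in the SAP, and one targeted query that may need source review because frequency is not among the AE items named in Protocol 7.3. TEAE counts may rise slightly.
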